4.1 Number of Participants

Thirty-six patients will be enrolled. We will screen approximately 400 patients within the eighteen-month period.

4.2 Number of Study Centers

This will be a single-center trial. Johns Hopkins All Children's Hospital will be the only participating hospital in this study.

4.3 Study Duration

We will begin screening patients after IRB approval of our pilot study. We will continue screening and inclusion in the trial until enrollment is met. We suspect this will take approximately eighteen months. The duration of participation will be approximately 30-days from the time of appendectomy. We will continue our pilot study until we have enrolled a total of 36 patients.

5 ELIGIBILITY CRITERIA

All children weighing equal to or greater than 20kg admitted to our institution with a diagnosis of acute appendicitis and who undergo urgent appendectomy will be eligible for this study. Patient and guardians will be approached with information about the study regardless of pre-operative categorization of appendicitis, suspected simple or suspected complex. The patient and family will be blinded as to which treatment arm they will receive.

5.1 Inclusion Criteria

- 5.1.1 Patient diagnosed with acute appendicitis and are scheduled to undergo urgent appendectomy
- 5.1.2 Patient is between 3-18 years of age at time of appendectomy
- 5.1.3 Patient has intraoperative findings of complex appendicitis defined by: visible hole in the appendix, extra-luminal fecalith, diffuse fibropurulent exudate outside the RLQ/pelvis, or intraperitoneal abscess
- 5.1.4 Patient weighs equal to or greater than 20kg at time of surgery

5.2 Exclusion Criteria

- 5.2.1 Patient is pregnant
- 5.2.2 Patient has a penicillin or cephalosporin allergy that is severe or anaphylactic in nature, prohibiting the use of these antibiotics
- 5.2.3 Patient has simple appendicitis
- 5.2.4 Patient who undergoes appendectomy following failed or planned medical management of appendicitis
- 5.2.5 Patient has impaired renal function (CrCl <15mL/min)
- 5.2.6 Patient has history of neurological conditions such as encephalopathy, seizures, myoclonus and non-convulsive status epilepticus
- 5.2.7 Patient has a known inability to complete a 30day postoperative follow up

6 ENROLLMENT GUIDELINES

Participants must meet all of the eligibility requirements listed in Section 5 prior to signing the IRBapproved informed consent form.

6.1 Screen Failures

Screen failures are defined as participants who consent to participate in the research but who are not subsequently randomized. Individuals who do not meet the criteria for participation in this study (screen fail) may not be re-screened.

7 ANTIBIOTIC INSTILLATION INTERVENTION PLAN

7.1 Intervention Schedule

All patients equal to or greater than 20kg presenting to Johns Hopkins All Children's Hospital with a diagnosis of acute appendicitis and are scheduled to undergo urgent appendectomy will be approached for participation in this study. Intra-operatively their eligibility to participate in the study will be determined. If complex appendicitis is found intra-operatively then the patient will be randomized into the control group (standard of care arm with intra-peritoneal fluid aspiration only), or the study group (intra-peritoneal fluid aspiration and antibiotic solution instillation). Antibiotic instillation will be introduced into the RLQ/pelvis after the appendectomy is completed and all intra-peritoneal fluid is aspirated. Ceftriaxone solution will be used depending on availability and pharmacy stock for use at Johns Hopkins All Children's Hospital. The ceftriaxone powder (1g) will be dissolved in 9ml of sterile normal saline. The entire contents of reconstituted powder will be fully withdrawn for a total instillation volume of 10ml. This fluid will then be instilled and left to dwell in the area of the peritoneal cavity where the appendix was removed.

Intervention

Standard of Care (Control group)/ARM A Intra-operative aspiration of intra-peritoneal fluid after successful appendectomy.

Standard of Care and Antibiotic instillation (Study group)/ARM B Intra-operative aspiration of intra-peritoneal fluid after successful appendectomy and subsequent instillation of 10ml of intra-peritoneal ceftriaxone (1g)

7.2 Third Generation Cephalosporin Intra-peritoneal Instillation Treatment

7.2.1 How Supplied, Stored, Packaged and Labeled

Ceftriaxone powder is stored in glass bottles in the OR Pyxis at room temperature with printed labels, noting dose and amount.

7.2.2 Preparation and Administration

The sterile ceftriaxone powder (1g) will be mixed with 9ml of sterile 0.9% normal saline. The entire contents of reconstituted powder will be fully withdrawn, for a total volume of 10mL. This solution will then be sterilely transferred to the surgical field and administered into the intra-peritoneal space under direct visualization prior to closure of the fascia.

7.2.3 Accountability and Compliance

Pending inclusion and randomization into the trial, the patient will be randomized into one of the two treatment arms. The patient will either receive the standard of care treatment arm, or the standard of care treatment arm with intra-peritoneal instillation of ceftriaxone. The amount of ceftriaxone used will be recorded in the patient's record in the EMR (Epic) by the circulating nurse in the operating room. The dose of ceftriaxone, and route will be verbally communicated to the operating surgeon who will agree with said treatment and document within their operative note.

7.3 **Prohibited Concomitant Medications**

Not applicable.

7.4 **Duration of Therapy / Intervention**

Participants must be withdrawn from the study treatment for the following reasons:

- Participant withdraws consent from the study treatment and/or study procedures. A participant must be removed from the trial at his/her own request or at the request of his/her legally acceptable representative. At any time during the trial and without giving reasons, a participant may decline to participate further. The participant will not suffer any disadvantage as a result.
- Participant is lost to follow-up.

• Death.

Participants may be withdrawn from the study for the following reasons:

- The participant is non-compliant with study drug, trial procedures, or both.
- If, in the investigator's opinion, continuation of the trial would be harmful to the subject's well-being.
- Development of a concurrent illness or situation which would, in the judgment of the investigator, significantly affect assessments of clinical status and trial endpoints.

7.5 Lost to Follow Up

A participant will be considered lost to follow up if s/he repeatedly fails to return for scheduled visits and is unable to be contacted by the study site. Before a participant is deemed lost to follow up, the investigator or designee must make every effort to regain contact with the participant. Where possible, three (3) telephone calls and a certified letter to the participant's last known mailing address per their medical record. These contact attempts will be documented in the research record.

8 TOXICITIES AND DOSE MODIFICATION

This study will utilize the CTCAE (NCI Common Terminology Criteria for Adverse Events) version 5.0 for adverse events and serious adverse event reporting. A copy of the CTCAE Version 5.0 can be downloaded:

https://ctep.cancer.gov/protocolDevelopment/electronic_applications/docs/CTCAE_v5_Quick_Reference_8.5x11.pdf

8.1 Adverse Events (AEs)

An adverse event is the appearance or worsening of any undesirable sign, symptom, or medical condition occurring after starting the **study intervention** even if the event is not considered to be related to study intervention. For the purposes of this study, the terms toxicity and adverse event are used interchangeably. Medical conditions/diseases present before starting study drug are only considered adverse events if they worsen after starting study intervention. Abnormal laboratory values or test results constitute adverse events only if they induce clinical signs or symptoms, are considered clinically significant, or require therapy.

AEs will be collected from the date of the operative intervention (with or without instillation of antibiotics) to 30 days after the operative date. Given the one-time study intervention and dosing timeline, any adverse effects should be seen well within the first 48 hours after administration. However, we will continue to review, document, and intervene on any adverse events that occur within the first 30 days following surgery.

Information about adverse events, whether volunteered by the participant, discovered by investigator questioning, or detected through physical examination, laboratory test or other means, will be collected, recorded, and followed as appropriate.

The occurrence of adverse events should be sought by non-directive questioning of the participant at each visit or phone contact during the study. Adverse events also may be detected when they are volunteered by the participant during or between visits or through physical examination, laboratory test, or other assessments. As far as possible, each adverse event should be evaluated to determine at a minimum:

- 1. The severity grade based on CTCAE v.5 (grade 1-5)
- 2. Its relationship to the study intervention (definite, probable, possible, unlikely, unrelated)
- 3. Its duration (start and end dates or if continuing at final exam)
- 4. Whether it constitutes an SAE

All adverse events are expected to be treated appropriately. Once an adverse event is detected, it will be followed until its resolution.

Information about common side effects already known about the commercial drug (third generation cephalosporin) is described in the Drug Information (section 3) and the FDA-approved product labels. This information is included in the participant informed consent and/or assent and will be discussed with the participant during the study, as needed.

All adverse events are recorded in the participant research chart.

8.2 Serious Adverse Events (SAEs)

Information about all serious adverse events is collected and recorded. A serious adverse event is one which meets any of the following criteria:

- Is fatal or life-threatening
- Results in persistent or significant disability/incapacity
- Causes congenital anomaly or birth defect
- Requires inpatient hospitalization or prolongation of existing hospitalization, unless hospitalization is for:
 - Routine treatment or monitoring of the studied indication, (such as ongoing pain, fever, constipation, bowel obstruction, surgical site infections, or other infections)
 - Elective or pre-planned treatment for a pre-existing condition that is unrelated to the indication under study and has not worsened since the start of study drug
 - Treatment on an emergency outpatient basis for an event not fulfilling any of the definitions of a SAE given above and not resulting in hospital admission
 - Social reasons and respite care in the absence of any deterioration in the participant's general condition
 - Is medically significant (i.e. defined as an event that jeopardizes the participant or may require medical or surgical intervention to prevent one of the outcomes listed above)

Events that fall within the definitions listed above must be reported as SAEs, irrespective of whether they are judged to be related to treatment or not. If an event is not an AE per the definition in section 9.1, then it cannot be an SAE, even if serious conditions are met (e.g. hospitalization, death due to progression of disease etc.). However, such events may meet JHM IRB reportable definitions as a UPIRSO (see section 9.3). Toxicities unrelated to treatment that

do NOT fall within the definitions above, must simply be documented as AEs in the participant research chart.

Collection of serious adverse events will begin after the patient is randomized into the study intra-operatively and will end 48 hours after administration of the intra-peritoneal antibiotics. It is very unlikely that any serious adverse event will occur given that this study intervention uses a commercially available antibiotic that is routinely administered both parenterally and locally. Adverse events due to intra-peritoneal antibiotic instillation may be difficult to distinguish given that similar antibiotics will be given intravenously.

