1 OBJECTIVES

1.1.1 Primary objective

To evaluate the feasibility and safety of the use of antibiotic solution instillation following intraoperative diagnosis of complex appendicitis. We will determine feasibility by the percentage of eligible participants who (1) agree to participate, and (2) complete all intervention sessions and measurement time points. Safety will be evaluated by adverse events associated with the use of intra-peritoneal antibiotic instillation for the treatment of peritonitis caused by complex appendicitis.

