2.1 Benefit / Risk Assessment

Appendicitis is one of the most common surgical diagnoses in the pediatric population and the most common surgical emergency in children.[1, 2] In complex appendicitis, the sequelae have progressed beyond the confines of the organ, and have led to purulent fluid in the intra-abdominal space, spillage of intestinal contents, or gross perforation of the appendix. Complicated appendicitis occurs in up to 20% of cases and is associated with a much higher morbidity and mortality. [5] Previous studies have shown that local treatment of peritonitis associated with PD catheters with intra-peritoneal antibiotics has had significant improvement of outcomes.[22, 23, 26, 28] The intra-peritoneal route is preferable as compared to oral and intravenous antibiotic administration due to elevated local levels of the antibiotic above the minimum inhibitory concentration while avoiding venipuncture and systemic side effects.[25, 26] There is minimal risk associated with involvement in this study given that we will be screening for any history of allergies to penicillin or cephalosporins, and excluding these patients. Ceftriaxone is commercially available, has a low risk profile, and is generally well tolerated with minimal side effects.

Our treatment period will include a one-time intra-operative dose of intra-peritoneal ceftriaxone. Typical dosing strategies for intra-peritoneal ceftriaxone administration occur on a daily basis, so our treatment period will also include the 24 hours following intra-peritoneal administration of ceftriaxone. All patients diagnosed with acute complicated appendicitis intra-operatively, and entered into our study, will also receive a minimum 48 hours of intravenous antibiotics as an inpatient, allowing for continued observation. We will be treating pediatric patients who are intra-

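### The hospitalization exemption and the 48-hour window in Section 8.2 leave SAE counts uninformative for infection and bowel obstruction

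*Combined protocol and SAP*

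**What the plan says.** Section 1.1.1 makes safety part of the primary objective: "Safety will be evaluated by adverse events associated with the use of intra-peritoneal antibiotic instillation". Section 12 repeats this and plans an incidence with a 95% confidence interval. It specifies no SAE analysis.

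Section 8.1 collects AEs from the operation to day 30 in both arms, related or not, and asks for each AE whether it is also an SAE.

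Section 8.2 calls an event serious if it meets any one of several criteria. One is "Requires inpatient hospitalization or prolongation of existing hospitalization, unless hospitalization is for", followed by a list of exceptions. The first exception is "Routine treatment or monitoring of the studied indication, (such as ongoing pain, fever, constipation, bowel obstruction, surgical site infections, or other infections". The section also has a criterion of medical significance, which takes in, among others, an event that "may require medical or surgical intervention to prevent one of the outcomes listed above". Events that meet the definition "must be reported as SAEs, irrespective of whether they are judged to be related to treatment or not". Collection starts at randomization and "will end 48 hours after administration of the intra-peritoneal antibiotics". Section 8.4 sends SAEs to the overall principal investigator and the IRB.

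Under Section 2.1, every enrolled patient receives a "minimum 48 hours of intravenous antibiotics as an inpatient, allowing for continued observation".

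**The concern.** Bowel obstruction, surgical site infection and infection in general are complications of the disease and the operation, not routine care of it. They are also harms one would want to watch closely when a drug is left in an infected peritoneum, a use that Section 2 describes as new. The phrase about other infections has no stated limit.

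At stake is the SAE record: the count a reader will look for, and the one event report to the IRB that needs no judgement about cause. If the definition screens out the expected serious complications, a low SAE count says nothing about whether instillation makes them more or less frequent. An imbalance between the arms could build up during the trial without producing a single SAE report.

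**Working it through.** The plan states no figure on this point, so there is none to reproduce. The check traces events through the rules and then shows the consequence with hypothetical counts.

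**Step 1: the time windows.** SAE collection closes 48 hours (2 days) after instillation. AE collection closes at day 30. The SAE window covers about 2/30 = 6.7% of the AE window. Section 4 schedules abscess imaging for patients still in hospital at POD 7 plus or minus 1 day, so at POD 6 at the earliest. That is 6 - 2 = 4 days after SAE collection has closed. Intravenous treatment in hospital lasts at least 48 hours after surgery, so discharge comes at about the time the window closes or later. A readmission would almost always fall outside it.

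**Step 2: the control arm.** SAE collection starts at randomization in both arms, but its end is counted from instillation. Arm A has no instillation (Section 7.1), so its 48-hour clock has no start and its closing time is undefined.

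**Step 3: events set against both rules.**

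| Event | Exempt from the hospitalization criterion? | Inside the SAE window? | Where it is still recorded |
|---|---|---|---|
| Prolonged index stay for fever, infection or obstruction, onset before 48 hours | Yes | Yes | AE; length of stay |
| Abscess found at POD 6 to 8 | Yes, if classed as a surgical site or other infection | No | AE; secondary outcome if drained |
| Readmission for infection or obstruction | Yes | No | AE; readmission rate |
| Fatal, life-threatening or disabling event | No | Only if before 48 hours | AE |

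In the first three rows no event becomes an SAE through hospitalization. Removing the exemption alone would rescue only the first row, and few of those: with a planned stay of at least 48 hours, prolongation will seldom be evident before the window closes. Extending the window alone would rescue none of the three through the hospitalization criterion. Both rules must change.

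**Step 4: what this does to the count (illustration only).** Assume that x of the 18 patients in one arm have an infection or obstruction, and that hospitalization is its only seriousness criterion. Exact (Clopper-Pearson) 95% intervals:

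- SAEs: 0/18 whatever x is. The upper limit is 1 - 0.025^(1/18) = 18.5%.
- Same events counted as AEs, x = 2: 2/18 = 11.1% (1.4% to 34.7%).
- x = 4: 4/18 = 22.2% (6.4% to 47.6%).
- x = 8: 8/18 = 44.4% (21.5% to 69.2%).

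The SAE line is the same in all three cases, while the AE line moves with the events. The values of x are assumptions that span a range; they do not come from the documents.

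**The case against.** The strongest reply is that nothing is lost from the trial's results. Primary safety is AE incidence, not an SAE count, and the exemption changes only the SAE label. Section 1.1.2 compares readmission and drained abscess by arm, Section 11.1 reviews deep organ space infection and complications, and Section 4 sets up an independent endpoint committee. All of this stands. A reader might infer that the primary safety result could look clean despite readmissions for infection; the documents do not support that.

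A reader might also see a contradiction, with a drained abscess exempt under one bullet and serious under another. There is none. One criterion is enough, and the exception qualifies hospitalization only, so an event exempt there can still qualify as medically significant. In the text available the medically-significant item sits among the exceptions. That may be a layout effect of the PDF, so it is a point to confirm, not an error.

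Nor does the exemption cover every infection: it is tied to routine care of the indication, and a fatal, life-threatening or disabling infection still meets the definition.

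Finally, the IRB has other sources of information. Section 8.3 requires prompt reporting of unanticipated problems, and Section 12 suspends the study after any AE secondary to instillation. But the first needs an event that is unexpected and signals greater risk, and the second needs attribution, which Section 8.2 concedes may be difficult because similar antibiotics are also given intravenously. An excess of expected complications in one arm could pass by both. SAE reporting is the route that asks neither question, and this part of the concern survives.

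**Conclusion.** The point holds for the SAE record and no further. The exemption and the 48-hour window together make SAE counts and SAE reports to the IRB uninformative for infection and obstruction, and the window has no defined end in the control arm. The exemption does not itself change the primary AE-incidence result.

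The number of patients affected cannot be stated. It is tempting to multiply 36 by a published abscess rate, but the documents give no rate of such events within 48 hours, and their highest figure is for deep space infection at any time. What can be said is structural: when hospitalization is the only seriousness criterion, the SAE count is zero however many such events occur. This assumes that investigators apply the exemption as written and that patients stay at least 48 hours.

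AE incidence, readmission and abscess by arm must therefore carry the safety assessment. Section 12 does not plainly say that it counts all AEs, since it speaks of those associated with instillation. That is a question of attribution, separate from the exemption, but the same amendment should settle it. The change should be made; it is not a fatal flaw.

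**What to change.** Reconcile Sections 8.1, 8.2 and 12 in one amendment:

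1. Limit the hospitalization exemption to an uncomplicated index stay, and delete the examples of obstruction and infection.
2. State that medical significance is a seriousness criterion of its own, not one of the exceptions.
3. Collect SAEs over the same 30 days as AEs, timed from surgery in both arms.
4. Tabulate all-cause AEs and SAEs by arm, with lines for readmission or prolonged stay due to infection, fever or obstruction.
5. If expected complications are to be spared expedited reporting, say so in Section 8.4, separately from the SAE definition.

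Items 1 and 3 must go together, since neither works alone. The cost is a wording amendment and some extra SAE forms. Patients are already followed to day 30 and the AE data are already collected, so no new visits or measurements are needed.

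### The end of SAE collection is tied to a dose that the control arm never receives, and in the treated arm it conflicts with the 30-day adverse event window

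*Combined protocol and SAP*

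**What the plan says.** Section 8.2 opens without a time limit: "Information about all serious adverse events is collected and recorded". It adds that events meeting its criteria "must be reported as SAEs, irrespective of whether they are judged to be related to treatment or not". Later in the same section, collection starts once the patient is randomised in the operating room and "will end 48 hours after administration of the intra-peritoneal antibiotics".

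Section 8.1 sets a different period for adverse events: "AEs will be collected from the date of the operative intervention (with or without instillation of antibiotics) to 30 days after the operative date". It says that drug effects should appear within 48 hours, but continues review to day 30 all the same. For each event, as far as possible, staff are to determine severity, relationship, duration and "Whether it constitutes an SAE". On ascertainment it says: "The occurrence of adverse events should be sought by non-directive questioning of the participant at each visit or phone contact during the study".

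Under Section 7.1, Arm A has aspiration of peritoneal fluid only and Arm B has aspiration plus one instillation. Section 8.4 sends SAEs to the principal investigator and the IRB. Section 12 (Analysis for Aim 1) makes safety part of the primary aim, reported as an incidence with a 95% confidence interval.

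**The concern.** There are two faults in one sentence. First, the end of the SAE window is defined by the intra-peritoneal dose, so it cannot be worked out for a patient who gets none. Site staff must supply their own rule for controls. If they use day 30, as 8.1 would suggest, controls are observed for SAEs over 30 days and treated patients over 48 hours, and SAE counts by arm are not comparable.

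Second, for a treated patient after hour 48, 8.1 still asks for a seriousness judgement while 8.2 has closed collection. Take a life-threatening event on day 10. It meets the first criterion in 8.2 ("Is fatal or life-threatening"), the hospitalisation exception does not remove it, and 8.1 would flag it as serious, yet it falls after the stated end of collection. Two careful coordinators could handle it differently.

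At stake are the completeness of SAE collection and reporting, and the meaning of any SAE table by arm. The pilot is meant to inform a larger trial and runs under an IND (Section 14.5), so that table is likely to be read closely.

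**Working it through.** The plan states no figure to reproduce. The check compares the windows and then measures the gap.

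**Inputs**
- Planned patients: 36, with 18 per arm (Section 12, Sample size justification).
- SAE window: from intra-operative randomisation to 48 hours after the intra-peritoneal dose (Section 8.2).
- AE window: from the operative date to 30 days after it, in both arms (Section 8.1).
- Arm A: no intra-peritoneal dose (Section 7.1).
- Inpatient intravenous antibiotics: at least 48 hours (Section 2.1).
- Outpatient follow-up points in the calendar: POD 14 and POD <30 (Section 9).

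**Step 1: can the end be calculated?**
- Arm B: yes, dose time + 48 h.
- Arm A: no, because there is no dose time. No other section gives an SAE end for controls. The nearest text is the monitoring paragraph of Section 12, which stresses the first 48 hours after surgery for all patients; it describes clinical monitoring and does not define SAE collection.
- Share affected: 18/36 = 50%.

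**Step 2: the gap in Arm B.** The dose is given during the operation, so both clocks start on the same day.
- 30 days × 24 h = 720 h
- 720 − 48 = 672 h, or 28 days
- 672/720 = 93.3% of the AE window lies outside the SAE window

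**Step 3: what falls in the gap.** Outpatient contact follows discharge, and discharge follows at least 48 hours of inpatient treatment. The Arm B window therefore closes at or before the earliest planned discharge. Both outpatient points (2 of 2) lie beyond it, although 8.1 directs staff to ask about adverse events at each contact. This follows from step 2 and is not a separate defect.

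**Step 4: do the time-unlimited sentences settle it?** The opening sentence of 8.2, its duty to report whatever the relatedness, and 8.4 all lack a 48-hour limit. They point the same way as 8.1 and against the cut-off sentence, so 8.2 is also inconsistent within itself.

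**Step 5: precision of a by-arm summary, if one is added.** The exact (Clopper-Pearson) 95% interval for 0 of 18 has upper limit 1 − 0.025^(1/18) = 18.5%, so it is 0% to 18.5%. For 2 of 18 (11.1%) it is 1.4% to 34.7%. Such a summary can only be descriptive.

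**The case against.** The best defence is that this is loose drafting with an obvious intent. The dose is given before the fascia is closed, so 48 hours after it is in practice 48 hours after surgery, a clock that can run in either arm and that Section 12 uses for monitoring everyone. Classifying events as serious to day 30 could coexist with a shorter, dedicated SAE collection period. Only collection is time-limited; the reporting sentences are not, so on the plain text a day-10 event flagged under 8.1 would still be reportable.

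There are also real safeguards:
- Adverse events are recorded in the research chart and followed to resolution.
- Unanticipated problems go promptly to the IRB.
- The suspension rule applies at any time and needs no SAE label.
- Readmission and drainage are 30-day outcomes.
- An independent endpoint committee reviews complications.
- Many late admissions for infection or obstruction come under the hospitalisation exception in 8.2.

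The safeguards stand, and they limit the harm. The intended-meaning argument does not remove the fault: a 48-hour clock from surgery is an inference about controls, not a stated rule. The unlimited reporting duty sharpens the contradiction, because staff would have to report events for which collection has ended. The endpoint committee's remit sets no SAE window.

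**Conclusion.** The concern holds. As written, the end of SAE collection cannot be applied to Arm A (18 of 36 planned patients). In Arm B it conflicts with 8.1 for about 28 of 30 days (93%). This assumes the planned 1:1 split and a dose given on the operative date.

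The consequence is confined to SAE collection, SAE reporting and any SAE table by arm. The incidence of adverse events keeps a common 30-day window, the seriousness criteria are defined, and no planned primary or secondary estimate changes. If the 8.1 seriousness item is completed, SAE counts to day 30 could be recovered. The documents give no SAE rate, so the number of events affected cannot be estimated. The sentence should be corrected, since safety is part of the primary aim, but it does not threaten the feasibility results.

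**What to change.** Replace the cut-off sentence in 8.2 with one window on a common anchor, for example: *SAEs are collected in both arms from randomisation to 30 days after the operative date.* A window of 48 hours after surgery in both arms, with the seriousness item in 8.1 aligned to it, would also remove the inconsistency. The 30-day version is better: it agrees with 8.1 and with the rest of 8.2, and it uses information already to be collected.

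A separate and optional addition to Aim 1 is to report, by randomised arm, the number and percentage of patients with any adverse event and with any SAE, regardless of attribution, with exact 95% intervals and labelled descriptive. It would sit beside the planned incidence of events associated with the instillation. It is useful because 8.2 concedes: "Adverse events due to intra-peritoneal antibiotic instillation may be difficult to distinguish given that similar antibiotics will be given intravenously".

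The cost is an IRB-approved amendment (Section 14.3), with case report forms updated if needed (Section 13). No new visits or data are required. Expect a somewhat higher SAE count and slightly more reporting to the principal investigator and the IRB, and possibly to the FDA under 8.4.
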